1.0 Objectives / Specific Aims

Pediatric burn injury remains a major public health problem, with approximately 120,000 serious pediatric burn injuries annually in the US [15]. Specialized burn center care, similar to medical services delivered at trauma centers, has been associated with improved survival, decreased hospital costs, and shorter lengths of hospital stay [16, 17]. The number of verified burn centers has decreased by 30% since the 1990s, leaving the majority of the US population living more than 2 hours by ground transportation to a verified burn center [18, 19]. 91% of pediatric burn patients are treated in the outpatient setting, often requiring multiple trips to the burn center to ensure that the burn heals without complication [20]. A second key factor in burn care is adherence to prescribed medical treatment. Poor adherence to therapy leads to an increased risk of infection and scarring and decreased range of motion [21-23]. Telemedicine is feasible in burn care [24-26] and facilitates the delivery of care to patients with burn injuries of all sizes [27]. Mobile health (mHealth) technology offers a promising approach to address these geographic barriers [28], but has never been used to provide expert burn care in the home.

A novel smartphone application for burn wound care, called the Telemedicine Optimized Burn Intervention (TOBI), was recently developed to enable burn experts to direct burn wound care while the patient and caregiver are home through text messaging and video-conferencing. The app was designed to bring expert wound care directly to the patient's home to address barriers to healthcare, including high cost burden and time commitment (e.g., geographic limitations, transportation to burn centers, parking, lodging, meals, time away from school and work), particularly for patients/families in rural and medically underserved communities (See Figure 1).

[figure not shown]

Figure 1. Burn App

The current ongoing Phase I study (**Pro00092341**) aims to refine TOBI, using qualitative research directed at stakeholder feedback, including caregivers and expert burn providers, to make the app/portal more "user-friendly." The ongoing project involves semi-structured interviews, assessment of satisfaction/usability and caregiver well-being and adjustment, and subsequent consumer-driven adjustments to the app to ensure high acceptability and usability. These adjustments will focus on improving patient adherence as well as provider barriers to implementation in preparation for a feasibility RCT.

Following optimization of TOBI app/portal, **the proposed feasibility RCT of burn care utilizing TOBI will be conducted.** The proposed study will recruit 64 patient/caregiver dyads from our pediatric burn center who are under outpatient medical treatment for a partial thickness burn and will randomly assign them to outpatient burn therapy enhanced with TOBI (TOBI) (n=32) vs. standard outpatient face-to-face (FTF) (n=32) therapy.

The **objective** of the proposed study is to assess the feasibility of the TOBI intervention and RCT research protocol in preparation for a subsequent large-scale multi-center RCT comparing outpatient burn care enhanced with TOBI vs. standard care. We will obtain preliminary indicators of effectiveness of the intervention rather than testing hypotheses. Clinical outcomes (burn healing, infection, change in therapy, adherence, and unexpected return to clinic/emergency room) will be assessed during baseline and at clinically determined intervals with (TOBI) or every clinic visit (FTF). We will also assess caregiver self-efficacy, stress, and well-being using psychometrically validated measures to understand whether these factors play a role in service utilization and outcomes. Many factors affect the successful implementation of an intervention that changes clinical practice, like TOBI [69]. The feasibility study is not sufficiently powered to make firm conclusions about TOBI's effectiveness, but will critically assist in identifying barriers to recruitment, retention, and procedures essential toward successfully conducting a large-scale, multicenter RCT. This is consistent with expert recommendations to test the feasibility of conducting an RCT while avoiding hypothesis-testing and yielding data to "debug" the methodology and assess optimal strategies for executing the RCT [69-72].

Aim 1: Assess feasibility of the proposed RCT methodology, including recruitment, participation and attrition, treatment fidelity, safety, and problems associated with equipment.

Aim 2: Obtain estimates of variability for the primary outcome measures: time to treatment of wound complication (e.g., infection, pain, non-healing), patient's sleep, therapy adherence, and FTF clinical visits. These variability estimates are needed to calculate sample size for a subsequent larger, adequately powered RCT to compare the effects of the TOBI intervention with FTF alone.

Aim 3: Examine factors related to caregiver attitudes toward telemedicine and access to health care, as well as caregiver stress, self-efficacy, and well-being in relation to treatment outcomes. Because caregivers randomized to TOBI will be the ones delivering burn treatment under the guidance of a provider through the app, they may experience elevated stress levels and anxiety, and their self-efficacy may influence treatment. Assessing these domains will strengthen our understanding of treatment utilization and outcomes as a function of caregivers' psychological factors. We also would like to assess post-injury caregiver adjustment from a more positive perspective (e.g., personal strengths, relating to others in times of need, spiritual change, appreciation of life), a construct that is conspicuously scarce in the scientific literature on caregivers of burn-injured children. Treatment feasibility and satisfaction will also be assessed.

The proposed mHealth intervention may (1) improve the quality of and access to expert burn care for pediatric surgical patients and their families and (2) relieve the burden on burn providers by allowing them to remotely direct treatment in the patient's home. TOBI has significant clinical utility and strong potential to influence access to care and alter the doctor-patient relationship, enabling healthcare providers to prescribe the right intervention at the right dose at the right time for each patient. Findings from this study will demonstrate the feasibility of testing a scalable, low-cost intervention in a multicenter RCT.

2.0 Background

Access to expert burn care: Pediatric burn injury affects more than 120,000 patients a year, the vast majority affecting children under 6 years of age [15]. Burns are severe injuries requiring highly specialized treatments. Since 1981, the number of accredited or verified burn centers has decreased by 29%, with only 51 centers nationwide verified by the American Burn Association (ABA), and 128 self-reported centers [18, 19, 29, 30]. Unfortunately, this decline in burn centers has led to decreased access to expert burn care for many patients, particularly the rural populations. Nationally, 25%, 46%, and 68% of the US population lives within 1, 2, or 4 hours of a verified burn center; while 41%, 68%, and 91% live within a self-described burn center, with regional variation [18]. Poor access to care is evidenced by inability to pay, lack of insurance, large distances from tertiary care facilities, inadequate knowledge, limited transportation resources and time constraints, especially for working families [31]. In addition, medically-vulnerable populations are more likely to experience inferior outcomes, more likely to have fewer health care choices, and less likely to see a specialist [32]. As burn care has become regionalized, so have the resources and expertise required for high quality care. Errors and delay in treatment occur when burns are treated outside of burn centers [18, 33, 34].

Outpatient burn wound care: ~91% of serious pediatric burn injuries (those requiring medical treatment) are partial thickness burns (See Figure 2) treated in the outpatient setting, with the majority of care occurring in emergency rooms and outpatient burn or plastic surgery clinics [20]. With increasing emphasis on cost saving, larger burns are increasingly being managed in the outpatient setting [35-37]. The goals of burn wound care are to minimize pain, decrease the risk of infection, promote healthy wound healing, minimize cosmetic deformities, and preserve function [20]. Standard outpatient therapy usually lasts 10-21 days, with the majority of pediatric partial thickness burns healing by 14 days [1]. During this period, the burn wound is assessed for complications including pain, infection, non-healing, and need for operative intervention, with repeat face-to-face clinic visits, one to three times per week, depending on the practice of the burn center [38].

[figure not shown]

Figure 2. Skin Burn Types.

Adherence to burn wound therapy: To promote recovery after burn injury, appropriate burn care (e.g., wound debridement, dressing changes, range of motion exercises) is critical [22]. Delays in care and poor adherence to prescribed therapies can lead to a higher risk of infection, hypertrophic scarring, contractures, and impaired range of motion [21, 23, 39]. Treatment adherence is defined as “the extent to which a person’s behavior coincides with medical or health advice [40]. In outpatient burn care, factors such as discomfort, physical limitations, and lack of information have been associated with non-adherence [39, 41, 42]. Another study demonstrated that having an “expectation of a positive result,” “social support,” “personal factors” (e.g., use of coping strategies, problem solving, information seeking) were the most common resources used by adults and children to increase adherence to burn care therapy [42]. Adherence of various aspects of burn care has been found to range from poor to good, primarily based on education of patients and communication between the multidisciplinary burn team and the patients and caregivers [23].

Telemedicine use in burn injury: Telemedicine, defined as the remote diagnosis and treatment of patients by means of telecommunication technology, has been used for two decades in burn care [43]. The assessment and treatment of burn injury are ideally suited for the use of telemedicine [24, 44-47]. A systematic review of telemedicine in burns [44] identified 24 studies, the majority with poor methodological detail and no a priori power calculations. Eight studies in the review found that digital imaging was comparable to FTF evaluation. Twelve studies demonstrated proof of concept for decreasing emergency air or ground transfer to burn centers through ER telemedicine carts, but these studies failed to show cost effectiveness and were retrospective. No high quality, prospective RCTs have been performed demonstrating the efficacy of telemedicine on the outcomes of burn patients. Unfortunately, the rapid rise of telemedicine in practice has not been followed by careful validation studies. The last Cochrane review on the effectiveness of telemedicine interventions found a continuing need for larger studies of telemedicine as controlled interventions, with more focus on patients’ perspectives with a specific need for collaborative work to generate innovation [48].

Role of mHealth in Burn Care: mHealth, the use of wireless technology in healthcare, is a rapidly growing field in the provision of medical care [49]. Cell phones are utilized by ~95% of adults in the US, with widespread dissemination in all groups irrespective of race/ethnicity, socioeconomic status, or urban-rural classification [50, 51]. Patients and

families are receptive to mHealth programs [52, 53]. To date, pediatric mobile device solutions surrounding the doctor-patient communication have focused on phone calls and SMS messaging related to chronic health conditions, but do not involve direct contact between doctor and patient [54, 55]. Mobile phones have surpassed the minimum requirements needed for burn assessment [56] but rigorous scientific validation to addressing outcomes has not been achieved [57]. A systematic review of smartphone applications in burns found 31 apps in the Google Play Store and 29 in Apple's App store [58]. The apps fell into 4 groups: calculators, information apps, book/journal apps, and games. One app uses store-and-forward images to aid remote doctors in evaluation of acute burns in the office setting [57]. No apps have been developed and evaluated to assist patients and families treating serious burn injury in outpatient settings.

Acceptability of mHealth in healthcare organizations: As patient-generated healthcare data gains traction in medical decision-making, both patients and providers are major stakeholders in the process and content. In [name] previous mHealth development work, he found patients desire reminder notifications, instructions and rationale explanations, customizable avatars, incentives and rewards, and clear communication lines, while providers value data management, tracking, and summaries [59, 60]. Increasingly, patients expect healthcare to be "on demand" and "user-friendly," while healthcare systems have lagged behind these expectations. Understanding these stakeholder tensions is imperative to the process of designing effective mHealth systems of care [8]. The rapid evolution of telemedicine has followed the pace of technological advancement, enabling health care entities to provide health care in ever-changing settings, often blurring the lines of traditional care, and thus, the roles of the health care provider [7].

Payer reimbursement of remote patient monitoring (RPM): Billing for physician-based telemedicine services has been a barrier to widespread adoption of telemedicine throughout the United States. Physicians performing telemedicine consultation services to patients remotely in outlying hospitals or clinics are now reimbursed at the same levels as in-person, known as parity, although there is still variation at the state level [61]. While there is no parity payment for physician services provided in the patient's home, Medicare and Medicaid have unbundled the CPT code 99091 to allow for clinician billing of RPM services, specifying the use of digital data transmitted to the physician, billed over a 30-day service period.

3.0 Intervention to be studied

Telemedicine, in various forms, is feasible in burn care [24-26] and facilitates the delivery of care to patients with burn injuries of all sizes [27]. Mobile health (mHealth) technology, offers a promising approach to address barriers [28], but has never been used to provide expert burn care in the home. Smartphone app-based burn injury care exists in practice, although rigorous scientific validation has not been achieved. The MUSC pediatric burn team has partnered with TACHL (Technology Applications Center for Healthy Lifestyles) to provide pediatric patients and their families with state-of-the-art burn care at home using a novel mobile health technology, called the Telemedicine Optimized Burn Intervention (TOBI). TOBI is a smartphone application synced with a portal used by providers, as an adjunct to standard therapy. This burn app provides education through frequently asked questions, instructional burn dressing change videos, and direct communication between patient and burn expert through store-and-forward pictures and videoconferencing.

The ongoing Phase I study (**Pro00092341**) builds upon our proof-of-concept study using a smartphone app to provide expert burn care to children in the home. Feedback from pediatric burn patients, parents, and their health care providers guided initial development and pilot testing of TOBI, which connects clinicians and caregivers through text-messaging, wound image transfer, and video-conferencing. We conducted an open trial (n=32) using TOBI and found high parental and provider acceptability and usability. Comparisons against a historical comparison group suggested quicker time to detect healing, fewer in-person clinical encounters, and greater adherence to treatment among families using TOBI vs. standard care [4]. Rigorous scientific study is needed to validate this novel clinical care pathway as mHealth technology shifts the fundamental structure of the provider-patient relationship. The ongoing Phase I study will culminate with evidence-based optimization of TOBI based on stakeholder feedback prior to the proposed RCT.

Innovation

TOBI is an innovative solution to improve access to expert burn care and adherence to burn therapy: The proposed research will capitalize on innovations in technology to improve the efficiency and effectiveness of outpatient burn care. There is a persistent gap between the care that is prescribed and that which is delivered in the outpatient setting [22, 23, 39]. The proposed work takes an innovative approach to meeting this need by increasing access to burn experts through mHealth technology and addressing adherence to prescribed treatment by increasing communication between provider and patients.

TOBI will be applicable and translatable to a broad range of pediatric surgical illness and traumatic illness: This line of work will refine a highly novel, quality of care solution that has strong applicability to a range of pediatric surgical treatments and populations. The use of outpatient burn care as a model intervention for this work is innovative because burn assessment and treatment is well-suited for telemedicine [24, 44-47]. Understanding the needs of patients and parents using the TOBI platform will ensure strong translatability to a wide range of chronic pediatric diseases may be amenable to mHealth remote patient monitoring (RPM), including pectus excavatum, intestinal failure, and adolescent morbid obesity.

TOBI will be a platform for tailoring and personalizing treatment to optimize outcomes: TOBI allows the physician and patient to make faster decisions regarding treatment rather than having the patients and families wait for scheduled clinic appointments, often hours away from home. mHealth offers a distinct advantage to answer the NIH Strategic Objective call for “precision medicine,” to enable healthcare providers to prescribe the right intervention at the right dose at the right time for each patient (Strategic Objective 1) [14].

TOBI is scalable, sustainable technology that overcomes traditional telemedicine barriers: While telemedicine has the potential to bring expert wound care directly to the patient in rural and medically-underserved communities [24, 62, 63], the traditional paradigm of a telemedicine hub-and-spoke model can be a financial burden to health care systems and inefficient for health care providers, leading to inconsistent adoption by hospitals and burn providers [64-66]. Building upon our study aimed at optimization of TOBI, the proposed Phase II study will allow us to explore implementation, scalability, and sustainability barriers with a population and a clinical problem that has not been explored in this way. Phase II study will be submitted as a separate IRB protocol.

4.0 Study Endpoints

Primary endpoints

- Feasibility outcomes:
 - Recruitment (ratio of how many recruited vs. consented; reasons why patients chose not to do the study);
 - Participation/attrition (percentage of those consented and retained over time vs. dropouts; or benchmark for attrition is consistent with similar studies and is 20%; reasons why patients dropped out and from which condition);
 - TOBI treatment fidelity (providers' adherence to the treatment protocol; will use a fidelity checklist each visit which will be self-rated by providers themselves and patients);
 - Safety (AE or SAE, UPs occurrence in both conditions),
 - Problems with technology (number of times problems happened, notes if TOBI did not function correctly [e.g., video breaks down]).

Secondary endpoints

- Clinical outcomes:
 - Time to treatment of wound complication (e.g., infection, pain, non-healing), patient's sleep, therapy adherence, and FTF clinical visits.
- Caregiver factors:
 - Attitudes toward telemedicine, perception of healthcare access, affect, distress/stress, depression, anxiety, self-efficacy, posttraumatic growth.
 - Satisfaction with care

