10.0 Study Design / Methods

The RCT will include 64 patient/caregiver dyads recruited from the MUSC outpatient burn clinic, hospital floor, or pediatric emergency room, randomized to burn care enhanced with TOBI (n=32) or FTF standard care (n=32). After obtaining informed consent, the research staff will create a new patient record in the REDCap database and assist (if needed) the caregiver in completing the initial questionnaire battery using the REDCap survey. The baseline questionnaires, completed by the caregiver, will include the demographics form, measures about attitudes toward telemedicine, perception of healthcare access, affect, depression, anxiety, self-efficacy, and peritraumatic distress (see measures attached). All PHI will be protected by a study ID to promote confidentiality. The family will receive a ClinCard at the beginning of the study which works like a bank debit card and can be used to purchase goods or services everywhere Debit MasterCard is accepted. Each time they receive payment for participation in this study, the money will be added to the card. Families will receive \$20 for completion of baseline assessment.

At the completion of questionnaires, caregivers will be randomly assigned to treatment conditions. Stratified permuted block randomization will be used to assign patients to either the burn care enhanced with TOBI or FTF care only (32 dyads per arm). Assignment will be stratified by provider to ensure balanced enrollment across the treatment arms regardless of numbers enrolled per provider. To minimize the likelihood that the blind will be broken, i.e. the next treatment assignment can be guessed, the block size will be varied.

Chart review will be conducted within approximately 72 hours of enrollment and data will be recorded in a chart review checklist and subsequently transferred into the database (e.g., burn mechanism, % TBSA, burn location, burn depth, date of burn injury, time to medical treatment, type of first clinical encounter [burn outpatient vs. emergency department vs. hospital discharge], and type of dressing).

Patients randomized to FTF will undergo standard burn care including a return follow-up in the burn clinic on a routine basis as prescribed by the clinical burn team (e.g., at least once per week) until the burn has healed. Healing is defined as greater than 95% epithelialization of the burn wound. This will be determined by a clinician.

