Clinical data will be collected on case report forms by the clinical care team (e.g., burn nurse, physician) and entered into the REDCap database in a coded manner by a research assistant (who is blind to the treatment condition to reduce bias during data entry) at clinically determined intervals per routine care based on clinical judgment with TOBI or FTF (see table below). The duration and number of clinical encounters for both conditions will be guided by best clinical practice and each patient's needs. On average, most burns that meet the study eligibility criteria require 2-5 visits and heal within 2-4 weeks. Case report forms will be generated with study ID only, with no identifiable PHI in order to protect patient's privacy. Data collected at intervals will include adherence to prescribed wound care, change in therapy, wound complications, day of healing, pain scores, sleep problems, unexpected return to clinic or emergency room (see Clinical Case Report Form attached). App metrics, such as number of videoconferences, number of text-messages, number of photos, and scripted messages by burn professional will be recorded by the app software and exported at the end of the study. Images of wounds will not be stored for the purposes of this study. They may be uploaded by clinical care team members into the patient's medical record as part of standard care procedures (outside of the study). Adherence to therapy will be defined as parent/patient performance of prescribed wound care through the end of treatment. Overall compliance with therapy is defined as documentation of healed burn through TOBI or FTF. Clinical data collection will continue until 1 month after the burn is diagnosed as healed by a burn physician in either condition (FTF or TOBI).

At 1-month, caregivers will be asked to complete the post-treatment questionnaires by phone or virtually using the REDCap survey, using a public link and study ID to identify their survey. This assessment will include measures about attitudes toward telemedicine, perception of healthcare access, affect, depression, anxiety, perceived stress, posttraumatic growth, treatment satisfaction, and app feasibility (TOBI only group) (see measures attached). Collected data will be entered into REDCap by the study staff. Overall, participation rate will be recorded. Families will receive \$30 following completion of post-treatment assessment.

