Data analyses will be performed by [name] and study coordinator at the completion of the study in aggregate in a blinded fashion to prevent bias as much as possible. Quantitative questionnaire and case report form data will be exported from REDCap and

analyzed using statistical software (e.g., SPSS). [name] will oversee [name] and the study coordinator in all data analyses.

TOBI	Data Collected	Enrollment	TOBI Video Visit 1	TOBI Video Visit 2	TOBI Video Visit 3	TOBI Video Visit 4	TOBI Video Visit X (possible)	End of therapy (1 month FU)
	Demographics Form	X						
	Chart review data (e.g., burn mechanism, % TBSA, burn location, burn depth, date of burn injury, time to medical treatment, type of first clinical encounter [burn outpatient vs. emergency department vs. hospital discharge], and type of dressing)	X within 72 hrs						
	Caregiver measures: - Attitudes toward telemedicine / technology - Perception of healthcare access - PANAS (affect) - PROMIS-Depression - PROMIS-Anxiety	X						X
	Caregiver measures: - PROMIS-General-Self-Efficacy - PROMIS-Self-Efficacy-Manage-Emotions - Peritraumatic Distress Inventory	X						
	Caregiver measures: - Perceived Stress Scale - Posttraumatic Growth Inventory							X
	Case Report Form: - Clinical endpoints, including pain score, healing, infection, change in therapy, adherence, sleep, unexpected return to ED/clinic	X	X	X	X	X		
	Caregiver satisfaction & usability surveys: - Satisfaction questionnaire - MAUQ (app usability) – TOBI only							X
	Post-treatment data: - Adherence to treatment - Total # of FTF visits - Total # of TOBI visits - Total travel time - Direct cost to patient/caregiver - Return to work/school date							X
	App metrics (# of video-conferences, messages, & photos) – TOBI only							X
FTF	Data Collected	Enrollment	Clinic Visit 1 (date)	Clinic visit 2 (date)	Clinic visit 3 (date)	Clinic Visit 4 (date)	Clinic Visit (possible)	End of therapy (1 month FU)

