focus on variability and precision of estimates rather than magnitude of effect sizes. 95% confidence intervals (CIs) of the difference in mean days to healing (or treatment change/infection) between interventions will be obtained. In addition, survival distributions and their 95% CIs will be obtained for each intervention arm using the Kaplan-Meier product limit method. Further, 95% CIs for hazard ratios will be obtained using Cox proportional hazards regression to model time to healing (treatment change) as a function of the intervention. In the future RCT, generalized linear mixed models (GLMM) will be used to obtain estimates of the variances of the clinical outcomes and the covariance structure of longitudinal measures as critical input information for determination of sample size (and hence adequate power) [82, 83]. Frequency distributions of AEs and SAEs will be used to characterize each intervention group. Analyses of caregiver data will include pre- and post-treatment group differences (TOBI vs. FTF) to understand factors related to caregiver well-being and adjustment following mHealth burn treatment and possible predictors of outcomes. These analyses may include mixed design repeated measures analyses of variance (ANOVAs) and regressions.

When the study is concluded, after 6 years all records related to the study will be destroyed. Furthermore, all staff will sign confidentiality agreements, and training sessions will emphasize the critical importance of confidentiality. The likelihood that these methods will effectively protect the confidentiality of participants is considered to be extremely high. Based on our experience with previous research projects, it is believed that these procedures will be effective in protecting confidentiality of subjects and minimizing any potential risk from participation.

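### Caregiver self-efficacy is listed as a secondary endpoint but is scheduled only before randomisation, so it can serve as a baseline predictor and not as an outcome

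*Combined protocol and SAP*

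**What the plan says.** Section 4.0 divides the secondary endpoints into clinical outcomes and caregiver factors. The caregiver factors are "Attitudes toward telemedicine, perception of healthcare access, affect, distress/stress, depression, anxiety, self-efficacy, posttraumatic growth", followed by satisfaction with care.

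Section 10.0 sets the timing. The baseline questionnaires cover, among others, "affect, depression, anxiety, self-efficacy, and peritraumatic distress (see measures attached". Allocation comes next: "At the completion of questionnaires, caregivers will be randomly assigned to treatment conditions". The 1-month survey is then listed item by item: "This assessment will include measures about attitudes toward telemedicine, perception of healthcare access, affect, depression, anxiety, perceived stress, posttraumatic growth, treatment satisfaction", with an app measure added for the TOBI arm only. Self-efficacy is not in that list. The schedule table agrees. The row holding "PROMIS-General-Self-Efficacy - PROMIS-Self-Efficacy-Manage-Emotions - Peritraumatic Distress Inventory" has a single mark, at enrollment, while the row above it (attitudes, access, PANAS, PROMIS depression and anxiety) is marked at enrollment and at the 1-month follow-up.

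For the analysis, Section 11.0 says: "Analyses of caregiver data will include pre- and post-treatment group differences (TOBI vs. FTF". It adds that the methods may include mixed-design repeated measures ANOVAs and regressions. No caregiver scale is named and none is excepted.

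**The concern.** A secondary endpoint in a randomised comparison is ordinarily something that treatment could change. A score taken before allocation cannot be changed by treatment. If self-efficacy were reported by arm as Section 4.0 implies, the table would be a check of baseline balance presented as a result.

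The gap has some practical interest. Aim 3 notes that TOBI caregivers will carry out burn treatment under remote guidance. Whether that raises or lowers their confidence is a reasonable question, and the present schedule cannot address it. The study's stated purpose is to find faults in the methods before a multicenter trial, so an endpoint without an outcome measurement is worth settling here and not carrying forward. A 1-month score that is not collected cannot be recovered later.

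**Working it through.** The plan gives no figure to reproduce. The check sets the endpoint list in Section 4.0 against the two batteries and the schedule table in Section 10.0.

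| Caregiver item in Section 4.0 | At enrollment, before allocation | At 1 month |
|---|---|---|
| Attitudes toward telemedicine | yes | yes |
| Perception of healthcare access | yes | yes |
| Affect (PANAS) | yes | yes |
| Distress/stress | Peritraumatic Distress Inventory | Perceived Stress Scale |
| Depression (PROMIS) | yes | yes |
| Anxiety (PROMIS) | yes | yes |
| Self-efficacy (two PROMIS scales) | yes | **no** |
| Posttraumatic growth | no | yes |
| Satisfaction with care | no | yes |

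Eight of the nine constructs have a 1-month measure, and self-efficacy is the exception. This counts distress/stress as one construct, as Section 4.0 writes it. The Peritraumatic Distress Inventory on its own is also collected only at enrollment, but Perceived Stress represents that construct at 1 month.

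The legible rows of the schedule table are those for TOBI. The finding does not depend on the FTF rows, because the prose of Section 10.0 describes both batteries for caregivers in general and restricts only the app measure to one arm.

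**What can be formed.** Write Y0 for the enrollment score and Y1 for the 1-month score.

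- Change within caregiver: Y1 − Y0. This needs Y1.
- Post-treatment contrast: mean Y1 in TOBI − mean Y1 in FTF. This needs Y1.
- Time-by-arm term in a mixed-design ANOVA: needs both Y0 and Y1.
- Between-arm difference in Y0: can be computed, but randomisation makes its expected value zero whatever TOBI does.
- Regression of a clinical outcome on Y0: can be computed, and it is a legitimate Aim 3 analysis.

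Scheduled values of Y1: 0 of 64 caregivers. The first three quantities are therefore unavailable and the last two are not affected.

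**What a 1-month measure would give.** Assume that loss matches the 20% attrition benchmark in Section 4.0 and is equal in the two arms. Then 64 × 0.80 = 51.2, or about 51 caregivers, would supply Y1, which is about 25.6 per arm. Before adjustment, the 95% interval for the between-arm difference would have a half-width of about 1.96 × √(2/25.6) = 1.96 × 0.280 ≈ 0.55 SD. Adjustment for Y0 would narrow it by an amount that depends on the correlation between Y0 and Y1, which the documents do not give. The estimate would be imprecise, as is normal for a feasibility study, but it would exist.

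**The case against.** The strongest reply is that self-efficacy was always meant as an explanatory variable. The objective in Section 1.0 says that caregiver self-efficacy, stress and well-being are assessed to see whether they bear on service use and outcomes. Aim 3 says of TOBI caregivers that "they may experience elevated stress levels and anxiety, and their self-efficacy may influence treatment", so stress and anxiety are what may rise and self-efficacy is what may act. The schedule fits this: anxiety is measured twice, perceived stress afterwards, self-efficacy beforehand. For a predictor, measurement before allocation is the better choice because treatment cannot have altered it.

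This stands, and it means that the schedule may be deliberate. It does not remove the inconsistency. If predictor use is the whole intent, the endpoint label in Section 4.0 is wrong. If an outcome is intended, the schedule is wrong.

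A reader might go further and infer that Section 11.0 commits the trial to a before-and-after test of self-efficacy, with the usual false-positive risk from comparing baseline scores. The documents do not support that. The Section 11.0 sentence is general and names no scale. It cannot cover every scale literally, since Perceived Stress and Posttraumatic Growth have no baseline value. No test or significance level is set for self-efficacy, and Section 1.0 says that the study seeks preliminary indicators and does not test hypotheses.

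Nor does any aim ask whether TOBI changes self-efficacy. The contrast between arms in the caregiver's role should also not be overstated: Section 10.0 defines adherence in both arms by what the parent or patient does in wound care, so FTF caregivers also deliver care at home.

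**Conclusion.** The mismatch is real and limited. Self-efficacy is declared a secondary endpoint, has one scheduled measurement before randomisation and none after it, and so cannot be evaluated as an outcome. It remains fully usable as a baseline predictor for Aim 3.

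The feasibility endpoints are unaffected. So are the Aim 2 variability estimates, which concern time to treatment of wound complications, sleep, adherence and FTF visits. The sample size was set on pragmatic grounds and does not depend on this measure. It would be too strong to say that the trial contains an invalid test or fails one of its aims.

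The conclusion assumes that the item-by-item 1-month list in Section 10.0 is complete as to self-efficacy. The schedule table supports this. Correction is worthwhile because it is cheap and because the missing 1-month data could not be obtained afterwards.

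**What to change.** Preferred change: add the two PROMIS self-efficacy scales to the 1-month REDCap caregiver survey in both arms, and mark them at that visit in the schedule table. In Section 11.0, state that the between-arm difference in the 1-month score will be reported with a 95% confidence interval, adjusted for the enrollment score, as an estimate and without a claim of effect. Keep the enrollment score as the Aim 3 predictor. The 1-month score should not take over that role, since treatment may have influenced it.

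The cost is a minor amendment and a small addition to a survey that already exists, using scales already in the study. The documents give no item counts, so the added time cannot be stated exactly. Caregivers whose 1-month survey is complete before the change would have no value, so the decision should come before follow-up surveys begin if possible.

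Alternative, if only predictor use is intended: relabel self-efficacy in Section 4.0 as a baseline predictor for Aim 3, and say in Section 11.0 that it is excluded from the before-and-after comparison of arms. This costs two short wording changes and adds nothing for caregivers to complete.
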